The opal body sensors (APDM, Opal, Portland, OR) will be fixed to each subject's wrists, ankles, sternum and lumbar spine and the SAW task will be carried out by the research coordinator for each combination of low and high frequency stimulation for the four contact pairs (total of 8 trials with each contact pair being either LFS or HFS, exclusively; refer to Figure 1). The gait measurements will be the same as in Phase I. Bradykinesia and tremor assessments will be conducted for each combination of stimulation and contact pairs using the Kinesia inertial sensors (Great Lakes Technologies, OH) as well. Ratings of items 3.1, 3.3 (a-e), 3.9, 3.11, 3.12, 3.13 of MDS-UPDRS III will also be conducted for each stimulation-contact pairing. Following each stimulation parameter change, there will be a 10-minute latency before the gait task is conducted. The participants will be blinded to each stimulation change.

During condition (2), the stimulators will be turned off and subjects will be given 1.5 times their usual levodopa dose (up to 300mg) to ensure transition to the medication ON state. Retesting will be done 1 hour after the levodopa challenge (or sooner based on patient report and visual confirmation by physician). Gait, bradykinesia and tremor sensor assessments as well as MDS-UPDRS III rigidity and axial subscore ratings will be conducted in the same manner as condition (1). The participants will be blinded to stimulation changes. At the completion of Visit 2, participants will return to their initial programming settings and resume their medication regimen as per their standard of care. If participant fatigue develops, he/she will have the option to complete condition (2) on another visit within a 4 week time period.

Beginning September 2020, and until the COVID-19 pandemic has passed, all subjects who are not fully vaccinated against COVID-19 will be tested for COVID-19 prior to participation (as outlined in Section 10.2). As a result, remote consent will be employed during the COVID-19 pandemic (see Section 8.2). COVID-19 tests will be performed by nasopharyngeal swab at a Northwell facility, the cost of which will be billed to the study fund.

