- Participants will be instructed to discontinue dopaminergic medications the night before each study visit, but they will remain on all other prescription medications. A drug-drug interaction is not anticipated during study participation with carbidopa/levodopa, as PD subjects, especially those with gait disorder, remain on some formulation of levodopa.
- Additional tablets will be administered (up to 1.5 times their usual dopaminergic dose) if wearing off is observed prior to the completion of study assessments.

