subscore ratings will be conducted in the same manner as condition (1). The participants will be blinded to stimulation changes. At the completion of Visit 2, participants will return to their initial programming settings and resume their medication regimen as per their standard of care. If participant fatigue develops, he/she will have the option to complete condition (2) on another visit within a 4 week time period.

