9 STATISTICAL CONSIDERATIONS

9.1 STATISTICAL HYPOTHESES

Aim 1. Our preliminary study established that gait and rest tremor are important factors to determine whether patients benefit from 60Hz stimulation or high frequency stimulation (38). However, the degree to which stimulation parameters affect gait parameters is not well established. In Aim 1, we will test the *hypothesis* that certain gait parameters are differentially affected between 60Hz and high frequency STN-DBS at various electrode contact configurations. In addition, in our preliminary analysis, we observed a modest reduction in dopaminergic medications in patients on 60Hz stimulation (12). Hence, we will also test the *hypothesis* that for some patients, the addition of levodopa in combination with 60Hz stimulation produces a synergistic improvement in certain gait domains.

Aim 2. Our preliminary data suggested that there is a link between the patient's baseline motor symptomatology measured by the MDS-UPDRS III ratings and the best stimulation frequency (60 Hz or HFS) chosen for the patient based on intensive clinical evaluations, which remained unchanged for an average of 12 months. In Aim 2, we test the *hypothesis* that a subject's gait kinematics on 60Hz stimulation can be predicted with statistically significant accuracy using gait measurements on high frequency stimulation. In addition, we will test the *hypothesis* that the best stimulation frequency (60Hz or HFS stimulation), which yields improvement among various gait parameters, can be predicted using objective sensor data collected at baseline. We define baseline motor performance as the severity of motor symptoms in the levodopa OFF and ON state without stimulation. In the remainder of this proposal, for simplicity we refer to 60 Hz stimulation and high frequency stimulation (130-180Hz) as low frequency (LFS) and high frequency (HFS), respectively.

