9.4.2 ANALYSIS OF THE PRIMARY EFFICACY ENDPOINT(S)

Aim 1.1.

Using the analytical software of APDM, the SWAY and TUG algorithms included in the SAW test will calculate asymmetry and variability for: postural sway (RMS AP & ML planes), cadence (CN), gait cycle duration, gait speed (SN), swing, double support, elevation at midswing, foot strike angle, toe off angle, stance, step duration, stride length (LN), arm swing velocity, arm range of motion, turn angle, turn duration, and turn velocity. All data will be tested for normality with Shapiro-Wilk test. Linear mixed models with repeated measures (LMMRM) will be used to compare high and low frequency over all contact pairs in the levodopa-OFF state. Parameter estimation will be based on restricted maximum likelihood and the form of the covariance matrix will be chosen based on Akaike's Information Criteria and Schwarz' Bayesian Criterion. The Holm-Bonferroni method will be used to adjust for multiple comparisons for the 20 outcome measures.

Aim 1.2. To investigate levodopa's effects on the gait domains, we will include the data for levodopa-ON and add a binary variable for levodopa (on or off) to the LMMRM from Aim1.1.

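### Aim 1.2: the levodopa main effect has no patient-by-levodopa error term, so its test could be anti-conservative if the model carries only a patient intercept

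*Combined protocol and SAP*

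**What the plan says.** The base model is set out under Aim 1.1 in Section 9.4.2: "Linear mixed models with repeated measures (LMMRM) will be used to compare high and low frequency over all contact pairs in the levodopa-OFF state". It is fitted by restricted maximum likelihood, and "the form of the covariance matrix will be chosen based on Akaike's Information Criteria and Schwarz' Bayesian Criterion". No candidate structures are listed.

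Aim 1.2 is a single sentence: "we will include the data for levodopa-ON and add a binary variable for levodopa (on or off) to the LMMRM from Aim1.1". It names no random effect for levodopa and no degrees-of-freedom method. It does not say whether the covariance form is chosen again on the combined data.

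Section 4.1 describes how the data arise. In the OFF state there is a "total of 8 trials with each contact pair being either LFS or HFS, exclusively". Then the stimulators are switched off and "subjects will be given 1.5 times their usual levodopa dose (up to 300mg) to ensure transition to the medication ON state", after which the assessments are repeated as in the OFF state. The ON part may be moved to another visit within four weeks if the participant tires. Section 6.1.2 adds: "Additional tablets will be administered (up to 1.5 times their usual dopaminergic dose) if wearing off is observed".

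The related hypothesis in Section 9.1 is that "for some patients, the addition of levodopa in combination with 60Hz stimulation produces a synergistic improvement in certain gait domains".

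**The concern.** Phase II has a split-plot structure. Frequency and contact pair change from trial to trial, but medication state changes once per patient. Whatever is particular to one patient's ON block (response to the challenge, individual dose, possibly a different day) is shared by all eight ON trials. Top-up tablets do not turn that block into independent applications of levodopa.

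A valid test of the average levodopa effect therefore compares it with the variation between patients in their ON-minus-OFF difference. A model with only a patient intercept compares it with trial-to-trial error instead. Standard errors would then be too small whenever patients differ in their response.

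The text points towards that model. In OFF-only data each patient has one medication state, so patient-by-levodopa variance cannot be separated from the patient intercept, and no AIC or BIC comparison on those data can find it. At stake is how often levodopa is declared to change a gait parameter in a primary sub-aim. The Holm-Bonferroni step is stated under Aim 1.1. Even if it carries over to Aim 1.2, it cannot repair p-values that are themselves too small.

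**Working it through.** **Inputs from the documents.** Eight trials per medication state, so 16 per patient (Section 4.1). Two-sided 5% level (Section 9.2). The sample size reproduces: 15.79 × 0.03 / 0.14² = 24.2, taken as 24, and 24 / 0.8 = 30. That gives 24 to 30 OFF/ON pairs, against 24 × 16 = 384 to 30 × 16 = 480 rows. The calculation compares walking speed between healthy people and people with Parkinson's disease, so it contains no within-patient variance.

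**Assumptions.** Residual SD 1. s is the SD of the patient-specific ON-minus-OFF difference, in residual SDs, from 0 to 1.0. The SD of the patient-specific frequency effect is f = 0.5. The true mean levodopa effect is zero.

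**Formula, patient-intercept-only model.**

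- True variance of one patient's ON-minus-OFF mean: s² + 1/8 + 1/8 = (1 + 4s²)/4.
- Variance the model assumes: m/4, where m is the pooled residual mean square. It absorbs a small share of the omitted terms: m ≈ 1 + 4s²/15 + 4f²/15.
- Ratio R = (1 + 4s²)/m. Type I error ≈ 2 × [1 − Φ(1.96/√R)]. The number of patients cancels.

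| s | 1 + 4s² | m | R | 1.96/√R | Type I error |
|---|---|---|---|---|---|
| 0 | 1.00 | 1.067 | 0.94 | 2.02 | 4% |
| 0.25 | 1.25 | 1.083 | 1.15 | 1.82 | 7% |
| 0.5 | 2.00 | 1.133 | 1.76 | 1.48 | 14% |
| 0.75 | 3.25 | 1.217 | 2.67 | 1.20 | 23% |
| 1.0 | 5.00 | 1.333 | 3.75 | 1.01 | 31% |

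Simulation of the same model agrees to within about one percentage point, with near-identical results at 24 and 30 patients. With f = 0 the rates are slightly higher (5% at s = 0, 32% at s = 1.0).

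**With a patient-by-levodopa term.** In balanced data the test is the paired t-test on each patient's ON-minus-OFF mean. Its simulated type I error is about 5% at every s.

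**With AIC/BIC selection on the combined data.**

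- Medication-block structure among the candidates: about 5% to 8%. The excess arises where the variance is small enough for selection to miss it.
- Candidates limited to compound symmetry, AR(1) and intercept plus AR(1): AIC selection gives about 11%, 18% and 30% at variance ratios r = s²/2 of 0.1, 0.3 and 0.7, that is s = 0.45, 0.77 and 1.18. These come from 300 fits each, so the Monte Carlo standard error is about 2 to 3 points.

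**Frequency-by-levodopa contrast, intercept-only model.** The block effect cancels between the two frequencies within each state, so the true variance does not grow with s while m does. Here R = 1/m. At s = 0.25, 1.96 × √1.083 = 2.04, giving 4.1%. At s = 1.0, 1.96 × √1.333 = 2.26, giving 2.4%. This contrast is conservative, not inflated.

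**The case against.** The strongest reply is that the plan does not treat trials as independent. It uses a repeated-measures mixed model with a data-driven covariance. Adding eight ON trials enlarges the covariance matrix, so applying the AIC/BIC rule again to the combined data is a natural reading, and nothing excludes a medication-block structure. This largely stands. A reader might infer that the eight ON trials are counted as eight independent replicates, but the documents do not say so. The reply still depends on two choices the plan leaves open: re-selection on the combined data, and inclusion of that structure among the candidates.

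Secondly, no variance component appears in the documents, so no single error rate can be attached to the plan. This stands too. A reader might take the inflated rates above as the operating characteristics of the planned test. They hold only for the assumed s and an intercept-only covariance.

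Thirdly, the statement in Section 9.1 that only some patients benefit concerns synergy with 60 Hz stimulation, which is an interaction. It is not direct evidence that the levodopa main effect varies between patients. That is fair, and a reader might wrongly conclude that the synergy test is inflated. Even so, individual capped doses, possible top-ups and a possible separate day for the ON block make identical ON-minus-OFF differences a strong assumption on which to rest a primary analysis.

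**Conclusion.** The concern holds as a conditional one. Followed literally, Aim 1.2 adds an on/off variable to a model whose covariance form is specified for data that cannot reveal patient-by-levodopa variance. With only a patient intercept, the type I error for the levodopa main effect could be roughly 7% to 31% for an assumed s of 0.25 to 1.0. It is not inflated if patients respond identically, and is about 5% to 8% if a block structure competes under AIC or BIC.

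The documents do not support an unconditional false-positive rate, or inflation of the frequency-by-levodopa contrast that carries the synergy hypothesis. Whether the model includes that interaction is a separate question. This is a specification that should be corrected before analysis; it does not invalidate the design.

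**What to change.** In Section 9.4.2, Aim 1.2, state that:

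- the model includes levodopa as a fixed effect and, irrespective of AIC/BIC, a random patient-by-levodopa (medication-block) effect;
- levodopa is tested with Kenward-Roger or Satterthwaite degrees of freedom, which in balanced data is the paired t-test on each patient's ON-minus-OFF mean;
- the remaining covariance form is chosen on the combined OFF and ON data, not carried over from Aim 1.1.

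A patient-by-frequency term does not substitute for the levodopa term, because it belongs to a different error stratum. The cost is a few lines of text and one extra variance component, with no additional patients, visits or assessments. Intervals for the levodopa main effect will be wider, but correct.

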1 PROTOCOL SUMMARY

1.1 SYNOPSIS

Title: Computational Modeling of 60 Hz Subthalamic Nucleus Deep Brain Stimulation for Gait Disorder in Parkinson's disease

Study Description: The goal of this research is to further our understanding and application of deep brain stimulation in Parkinson's patients with gait disorder.

We will assess the degree to which stimulation parameters affect gait parameters. We will test the hypothesis that the addition of levodopa in combination with stimulation produces a synergistic improvement in certain gait domains. In addition, we test the hypothesis that a subject's gait on stimulation can be predicted with statistically significant accuracy using gait measurements on high frequency stimulation. Finally, we will test the hypothesis that the best stimulation frequency, which yields improvement among various gait parameters, can be predicted using objective sensor data collected at baseline

Objectives:

Aim 1: To determine the impact of 60Hz subthalamic deep brain stimulation on gait kinematics using wearable sensors

- Aim 1.1: To determine whether 60Hz STN-DBS elicits a differential response in gait kinematics compared to high frequency
- Aim 1.2: To determine the influence of 60Hz STN-DBS and levodopa on gait kinematics

Aim 2: To develop machine learning models to predict optimal subthalamic deep brain stimulation frequency based on wearable sensor profiles of baseline Parkinson's motor symptoms

- Aim 2.1: To develop machine learning models to predict gait response to 60Hz stimulation without additional testing
- Aim 2.2: To develop machine learning models to predict best stimulation frequency (60Hz vs. high frequency).

Endpoints:

Primary Endpoints:

Gait parameters:

- Postural sway – root mean square (RMS) sway in antero-posterior (AP) and medio-lateral (ML) planes;
- Gait – cycle duration (seconds), speed (m/s), stance (%), swing (%), heel strike angle (degrees), toe off angle (degrees), stride length (cm), cadence (steps/min), step duration (seconds), elevation at midswing (cm) (foot clearance), double support (%), arm swing velocity (deg/s), and range of motion (degrees);

- Circumduction – turn angle (degrees), turn duration (seconds), and turn velocity (deg/s).

Machine learning models to: 1) predict gait kinematics on 60Hz STN-DBS; 2) predict best stimulation frequency using wearable sensor data collected at baseline.

Secondary Endpoints:

Tremor (rest, kinetic, postural)

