1.2 SCHEMA

Overview of the study design: **Figure 1:** For subjects undergoing STN-DBS implantation, Phase I will be preoperative (study visit 1), and Phase II will be 12-15 weeks post initial programming (study visit 2). For chronic DBS patients, Phase II will commence during study visit 1.

[figure not shown]
[figure not shown]

Figure 2. Overview of Aim 2 and the analysis to be performed.

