Phase II. The primary goal of Phase II is to investigate the impact of stimulation frequencies (low and high), stimulation spatial characteristics and levodopa on gait kinematic domains. Participants will be evaluated in two conditions: 1) OFF medication/ON stimulation; 2) ON medication/ON stimulation. Patient's weight will be collected prior to this assessment. For chronic DBS patients, phase II will commence during study visit 1. For preoperative subjects, phase II will be conducted on a separate visit (study visit #2) that will take place 12-15 weeks after initial programming of bilateral STN deep brain stimulation implantation. This visit will also be conducted in a laboratory setting. The impact of the lesion effect from the surgery would also be avoided with this timeframe.

During condition (1), patients will be evaluated following overnight withdrawal of dopaminergic medications. Afterwards, each electrode contact will be reprogrammed by the Lead Principal Investigator in both low frequency and HFS. For each of the 4 contacts on both electrodes, the amplitude will be slowly increased by 0.1-V increment until sustained sensory or motor side effects are produced in HFS. The amplitude below the side effect threshold will be used along with a standard pulse width of 60 μ s. For low frequency stimulation (LFS) programming, milliamps will be adjusted to keep the

total electrical energy delivered (TEED) between both LFS and HFS conditions equivalent for each respective contact. The TEED is calculated as milliamp² x frequency x pulse width/impedance (47).

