6.1.2 DOSING AND ADMINISTRATION

During Phase I, participants will receive no stimulation. For those subjects with chronic DBS, their stimulators will be turned off for at least 50 minutes to ensure adequate "wash-out" of stimulation effects prior to the assessment in each condition. If symptoms become intolerable, the wash out period may be shortened. This will be determined by the PI on a case by case basis. During Phase II, the Lead Principal Investigator will reprogram each electrode contact pair in both 60Hz frequency and high frequency stimulation (HFS). For each of the 4 contacts on both electrodes, the amplitude will be slowly increased by 0.1-V/mA increment until sustained sensory or motor side effects are produced in HFS. The amplitude below the side effect threshold will be used along with a standard pulse width of 60 μ s.

In both Phases, participants will be assessed in the practically defined levodopa OFF condition--whereby they will have their overnight dopaminergic medications withdrawn--and the Levodopa ON condition, in which participants will be given 1.5 times their usual levodopa dose (up to 300mg) using carbidopa/levodopa 25/100 tablets with water.

SINEMET tablets are available in a 1:4 ratio of carbidopa to levodopa (SINEMET 25-100) as well as 1:10 ratio (SINEMET 25-250 and SINEMET 10-100). Tablets of the two ratios may be given separately or combined as needed to provide the optimum dosage. Studies show that peripheral dopa decarboxylase is saturated by carbidopa at approximately 70 to 100mg a day. Patients receiving less than this amount of carbidopa are more likely to experience nausea and vomiting. The optimum daily dosage of Sinemet must be determined by careful titration in each patient.

- This dosage schedule provides 75 mg of carbidopa per day.
- The patient should be informed that Sinemet is an immediate-release formulation of carbidopa/levodopa that is designed to begin release of ingredients within 30 minutes.
- All study participants will be on a levodopa regimen. They will be given 1.5 times their usual dopaminergic dose in the form of the study drug with 3 tabs being the maximum dosage. This is in line with the standard of care in assessing the transition of a Parkinson's patient from the OFF levodopa state to the ON state in a controlled setting.
- Study drug will be taken at the research site by mouth with water.

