Aim 2.1. We will utilize the raw data collected during Phase II to develop regression models, under both ON and OFF medication states for all contact pairs. The top panel in Figure 2 presents the overview of Aim 2.1; the goal of this sub-Aim is to predict the gait parameters for patients on low frequency by using the gait sensor measurements obtained on high frequency. Additional independent variables/regressors include general patient/disease characteristics such as age, gender, and disease duration. We will also build models under both ON and OFF medications. To develop the regression models, we use non-linear regression analysis based on random forest (RF) classifier. RF is based on an ensemble of decision trees, referred to as a 'forest,' where predictions for any new observation are obtained from averaging the predictions of individual trees (56). Generally, RF models are not prone to overfitting and are robust against noisy or high-dimensional datasets (57). In addition, they are generally interpretable, allowing for further examination of results and easier subject subtyping with respect to symptomology. However, to assure that the RF based models are the best performing models, we also develop models based on some of the other machine learning techniques, such as neural networks (56), and use them as benchmarks. If needed, to improve model performance we will perform model building in RF models to identify and include the most important parameters (38). We will use techniques such as cross-validation (e.g., leave-one-out) and bootstrapping to examine the generalizability of the models and acquire confidence intervals for the predicted values. Lastly, we will compare the best performing models obtained for both ON and OFF medications and their most important contributing parameters to further investigate the interaction of medications and stimulation frequency.

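### Aim 1.2 names no frequency-by-levodopa term, so the hypothesis of synergy between levodopa and 60 Hz stimulation has no prespecified test

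*Combined protocol and SAP*

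**What the plan says.** The synopsis (section 1.1) undertakes to test the hypothesis that "the addition of levodopa in combination with stimulation produces a synergistic improvement in certain gait domains". Section 9.1 narrows this to 60 Hz and to a subset of patients: "for some patients, the addition of levodopa in combination with 60Hz stimulation produces a synergistic improvement in certain gait domains".

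The matching analysis is one sentence in section 9.4.2. For Aim 1.2 the levodopa-ON data are included and the analyst will "add a binary variable for levodopa (on or off) to the LMMRM from Aim1.1". The Aim 1.1 model compares high and low frequency over all contact pairs in the levodopa-OFF state. Multiplicity is addressed in the Aim 1.1 paragraph only: "The Holm-Bonferroni method will be used to adjust for multiple comparisons for the 20 outcome measures".

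One other analysis sentence mentions an interaction. Under Aim 2.1, the best-performing ON and OFF medication prediction models are compared "to further investigate the interaction of medications and stimulation frequency".

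On the data available, section 4.1 says of Phase II: "Participants will be evaluated in two conditions: 1) OFF medication/ON stimulation; 2) ON medication/ON stimulation". Section 6.1.2 says of the baseline phase: "During Phase I, participants will receive no stimulation".

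**The concern.** Synergy means that the joint effect differs from the sum of the separate effects. In a regression model that is an interaction. A model with a frequency effect and a levodopa effect, and nothing else linking them, sets the contrast (60 Hz ON − 60 Hz OFF) − (HFS ON − HFS OFF) to zero by construction. Following the plan as written would therefore yield no estimate, confidence interval or test for a hypothesis that the protocol says it will test on its primary endpoints.

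The comparator is also undefined. Section 9.1 refers to 60 Hz and the synopsis to stimulation in general. Neither says whether synergy is judged against HFS or against no stimulation.

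Two things could follow. An interaction term might be added after 20 outcomes have been seen, which would be post hoc. Or a reader might compare the OFF-only Aim 1.1 estimate with the pooled Aim 1.2 estimate, an unplanned comparison without error control.

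**Working it through.** **The plan's own figure.** Section 9.2 gives n = 24 from n = 2(Zα + Z1−β)²σ²/Δ², with σ² = 0.03 and Δ = 0.14 m/s. Putting the numbers in: 2 × (1.96 + 0.8416)² × 0.03 / 0.14² = 15.70 × 0.03 / 0.0196 = 24.03. This reproduces. It is sized on a healthy-versus-Parkinson's difference in gait speed, and no figure is given for an interaction.

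**What the additive model can see.** Take a balanced 2×2 with cell means in the order HFS OFF, HFS ON, 60 Hz OFF, 60 Hz ON. All effect sizes here are assumed (m/s). In the additive fit, the frequency effect is the mean of the two 60 Hz cells minus the mean of the two HFS cells. The levodopa effect is the mean of the two ON cells minus the mean of the two OFF cells.

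| Cell means | True interaction | Additive frequency | Additive levodopa |
|---|---|---|---|
| 0, 0.05, 0, 0.05 | 0 | 0 | 0.05 |
| 0, 0, −0.05, 0.05 | 0.10 | 0 | 0.05 |
| 0, 0, 0, 0.05 | 0.05 | 0.025 | 0.025 |
| 0, 0, 0, 0.10 | 0.10 | 0.05 | 0.05 |
| 0, 0, 0, 0.14 | 0.14 | 0.07 | 0.07 |

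Rows 1 and 2 differ only in whether synergy exists, yet both planned effects are identical. In rows 3 to 5 synergy s sits only in the 60 Hz + levodopa cell. The model then reports s/2 as a frequency effect and s/2 as a levodopa effect, and no parameter equals s. The OFF-only Aim 1.1 model correctly returns 0 for frequency in rows 3 to 5.

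**Simulation check.** This used 24 patients × 16 cells and 200 runs per scenario, with assumed between-patient SD 0.14 and residual SD 0.10.
- Row 1 truth: the additive model gave frequency 0.001 and levodopa 0.049. The model with the product term gave an interaction of −0.001, rejected in 6% of runs.
- Row 2 truth: the additive model gave frequency 0.000 and levodopa 0.051. The product term was estimated at 0.103, rejected in 99.5% of runs.

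In the additive model the levodopa effect was significant in every run of both scenarios, so that result says nothing about synergy.

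**Whether another section fills the gap.**
- Aim 2.1 compares random forest models and their important parameters. It names no contrast, statistic or alpha.
- Aim 2.2 predicts gait at both frequencies, ON and OFF medication, with bootstrap intervals, but again names no contrast.
- Section 9.4.7 covers subgroups by age, gender and disease duration only.
- Section 9.4.9 plans no exploratory analyses.

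**Precision of the missing test.** Treat the interaction as one contrast per patient and use a two-sided one-sample t test (noncentral t).

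| n | Alpha | Standardised contrast for 80% power |
|---|---|---|
| 24 | 0.05 | 0.597 |
| 24 | 0.05/20 = 0.0025 | 0.877 |
| 24 | 0.05/40 = 0.00125 (pooled with Aim 1.1) | 0.937 |
| 30 | 0.05 | 0.529 |
| 30 | 0.0025 | 0.767 |

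At an assumed standardised contrast of 0.5 with n = 24, power is 65% at 0.05 and 21% at 0.0025.

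On the speed scale, assume total variance 0.03, within-patient correlation ρ and no patient-level variation in the interaction. The contrast SD is then 2√(0.03(1 − ρ)). For ρ = 0.5, 0.7 and 0.9, the detectable interaction at n = 24 is 0.146, 0.113 and 0.065 m/s unadjusted, and 0.215, 0.166 and 0.096 m/s at the first Holm step.

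**The case against.** The strongest reply is that this is brevity, not error. Aim 1.2 is one summary sentence, no model equation is given even for Aim 1.1, and the wording does not forbid a product term. Interest in the interaction is visible in section 2.1 and under Aim 2.1, and Aim 2.2 would give predictions with intervals for all four frequency-by-medication conditions. The Aim 1.2 objective speaks only of influence, which main effects partly serve. All cells are collected, so nothing is lost for good.

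Much of this is fair. The fault is that the term is not specified, and the claim about the contrast being zero holds for the model fitted as written. But prespecification means naming the term, and the Aim 2 work provides intervals for predicted values, not for a difference of differences. The hypothesis in sections 1.1 and 9.1 is synergy, and main effects do not test it.

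Three further points stand as limits:
- The effect sizes and SDs above are assumptions. The 0.14 m/s in section 9.2 is not a synergy size, and power depends on the inputs. With residual SD 0.10, patient-level interaction SD 0.10 and synergy 0.10, the standardised contrast is 0.10/√(0.10²/4 × 4 + 0.10²) = 0.71, and power at n = 24 is 91% and 54%.
- The ON session follows the OFF session and may move to another visit within 4 weeks, and section 6.3 describes no randomised trial order. An interaction estimate could therefore carry time-since-dose or fatigue effects if the frequencies are not balanced within the session.
- The comparator has to be settled before the term is called the synergy test.

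**Conclusion.** The concern holds. The protocol commits to testing synergy, and its only Aim 1 analysis of the levodopa-ON data cannot test it as written. Two truths that differ by 0.10 m/s in synergy give the same planned effects. This should be corrected before the analysis, because it leaves a stated hypothesis on primary endpoints without a prespecified estimate, interval or test.

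Aim 1.1 is not affected, and the planned sample size is not disputed here. The algebra rests on a balanced 2×2 and on reading the Aim 1.2 sentence literally. The power figures rest on assumed standardised contrasts, because the documents give no within-patient SD.

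**What to change.** 1. State the comparator for synergy first. If it is HFS, the frequency-by-levodopa contrast answers whether levodopa adds more at 60 Hz than at HFS. That contrast would be zero if both frequencies were equally synergistic with levodopa. If the comparator is no stimulation, Phase II has no such condition. The Phase I stimulation-off records, OFF and ON levodopa, could then serve as a supporting analysis. Two caveats should be stated: these records are pre-implant for preoperative patients, and the wash-out may be shortened in chronic patients.
2. Add frequency × levodopa to the Aim 1.2 mixed model. Prespecify its coefficient, with confidence interval, as the Aim 1.2 test for the HFS comparison.
3. State the multiplicity family. A Holm adjustment across the 20 outcomes, separate from Aim 1.1, is one reasonable choice.
4. Because section 9.1 refers to some patients, report a patient-level random slope for the interaction where it can be estimated. There are 2 frequencies × 4 contact pairs × 2 medication states = 16 planned cells per patient.
5. State how trial order and time since dose will be handled or reported.

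A frequency-by-contact-pair term in Aim 1.1 is optional. It is needed only if the reference to contact configurations in section 9.1 is meant as effect modification.

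The cost is SAP wording; no new data are needed. The real limit is precision, so the interaction should be reported with its interval and described as possibly inconclusive.
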